5.6 Rule of exclusion criteria of analysis sets

Patient classification in the analysis sets is entirely based on protocol deviation and non-protocol deviation criteria. Details are provided in [Table 5-7](#) and [Table 5-8](#).

Table 5-7 Protocol deviations that cause patients to be excluded

Deviation ID	Description of Deviation	Exclusion in Analysis sets
EXCL01	Patients with primary progressive MS or non-relapsing/no MRI activity-SPMS	Excluded from PPS
EXCL02	Patients meeting criteria for neuromyelitis optica	Excluded from PPS
EXCL03	Disease duration of more than 10 years in patients with EDSS score of 2 or less	Excluded from PPS
EXCL08	Patients with an active chronic disease (or stable but treated) of the immune system other than MS or with a known immunodeficiency syndrome	Excluded from PPS
EXCL19	Teriflunomide (if discontinued for reasons related to safety or lack of efficacy) at any time prior to randomization	Excluded from PPS
EXCL25B	Patients currently treated with leflunomide	Excluded from PPS
EXCL49	History of clinically significant CNS disease (e.g. stroke, traumatic brain or spinal injury, history or presence of myelopathy) or neurological disorders which may mimic MS	Excluded from PPS
EXCL52	History of hypersensitivity to any of the study drugs or excipients (including lactose intolerance) or to drugs of similar chemical classes	Excluded from PPS
INCL01	Informed consent obtained = 'No' or missing	Excluded from all analysis sets
INCL03	No diagnosis of MS as defined by 2010 revised McDonald criteria	Excluded from PPS
INCL06	Neurologically stable within 1 month prior to randomization	Excluded from PPS
WITH11	Patient diagnosed with PML and study treatment was not discontinued	Excluded from PPS
TRT01	Patient received incorrect study drug	Excluded from PPS
TRT02	Patient received damaged or expired study drug	Excluded from PPS
COMD01	Immunosuppressive/chemotherapeutic medications or procedures, including	Excluded from PPS

Deviation ID	Description of Deviation	Exclusion in Analysis sets
	cyclosporine, azathioprine, methotrexate, cyclophosphamide, mitoxantrone, lymphoid irradiation and hematopoietic stem cell transplantation while taking double-blind treatment	
COMD02	Monoclonal antibodies targeting the immune system, including but not limited to natalizumab, alemtuzumab, and B-cell depleting agents such as rituximab, ocrelizumab and obinutuzumab while taking double-blind treatment	Excluded from PPS
COMD03	Any other immunomodulatory or disease- modifying MS treatment, including but not limited to, fingolimod, interferon beta, glatiramer acetate, dimethyl fumarate or systemic corticosteroids (except when given for MS Relapse treatment) while taking double-blind treatment	Excluded from PPS
COMD04	Leflunomide while taking double-blind treatment	Excluded from PPS
COMD06	Daclizumab while taking double-blind treatment	Excluded from PPS
OTH01	EDSS rater acted as a treating physician or treating physician acted as EDSS rater	Excluded from PPS
OTH02	Not following per protocol blinding procedures such that the integrity of the study is compromised	Excluded from PPS

Table 5-8 Patient Classification

Analysis Set	PD ID that cause patients to be excluded	Non-PD criteria that cause patients to be excluded
SCR	NA	NA
FAS	INCL01	Not assigned a valid randomization number Mis-randomized patients who didn't take study drug
PPS	As listed in Table 5.7	Not in FAS;

Analysis Set	PD ID that cause patients to be excluded	Non-PD criteria that cause patients to be excluded
		Compliance to study drug administration < 80%
		EDSS baseline value >=7.0
SAF	INCL01	No double-blind study drug taken

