5.5.7 Concomitant medication

The Investigator must instruct the patient to notify the study site about any new medications he/she takes after the patient was enrolled into the study. All medications (including dose changes), procedures and significant non-drug therapies (including physical therapy and blood transfusions) administered after the patient was enrolled into the study must be recorded in the concomitant medications / surgical and medical procedures CRF.

Each concomitant drug must be individually assessed against all exclusion criteria/prohibited medication. If in doubt the Investigator should contact the Sponsor Medical Advisor before randomizing a patient or allowing a new medication to be started.

If a patient is receiving dalfampridine (Ampyra[®]) concomitantly with study drug, the patient should remain as far as possible on stable dose throughout the Treatment epoch.

Based on the double-blinded design, the Investigator will need to consider the drug interaction potential of teriflunomide when study drug is co-administered with certain classes of drugs (refer to list of drugs and potential interactions in [Appendix 4](#)).

Premedication prior to sc injection

Premedication with acetaminophen and/or antihistamines (or equivalent) is recommended and may be administered at the discretion of the Investigator. For the first injection only, the addition of premedication with steroids (methylprednisolone 100 mg iv or equivalent) is recommended. Premedication should be administered 30 to 60 minutes prior to study drug injection.

Any administration of premedication must be recorded in the Prior and Concomitant medications CRF.

Additional information in regards to premedication for home-administration use:

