5.5.8 Prohibited medication

Use of the treatments displayed in [Table 5-1](#) is NOT allowed in combination with study treatment, due to increased risk of immunosuppression and confounding of efficacy evaluations.

Exclusionary medications for study eligibility are listed in the exclusion criteria ([Section 4.2](#)). Use of excluded medications is not allowed after randomization while the patient is on study medication.

Table 5-1 Prohibited medication

Medication	Additional action to be taken
Immunosuppressive/chemotherapeutic medications (including herbal) or procedures, including but not limited to cyclosporine, azathioprine, methotrexate, cyclophosphamide, mitoxantrone, lymphoid irradiation and hematopoietic stem cell transplantation	Discontinue study treatment, increase vigilance regarding infections. NOTE: Restarting study treatment in patients exposed to these medications is not permitted.
Monoclonal antibodies targeting the immune system, including but not limited to natalizumab, alemtuzumab, daclizumab and B-cell depleting agents such as but not limited to rituximab, ocrelizumab and obinutuzumab	Discontinue study treatment, increase vigilance regarding infections. NOTE: Restarting study treatment after exposure to B-cell depleting agents is not permitted. For others only after consultation with the Sponsor Medical Advisor.

Medication	Additional action to be taken
Any other immunomodulatory or disease-modifying MS treatment, including but not limited to fingolimod, interferon beta, glatiramer acetate, dimethyl fumarate	Discontinue study treatment, increase vigilance regarding infections.
Systemic corticosteroids (except for when given for MS relapse treatment as defined in Section 5.5.6).	Interrupt study treatment, increase vigilance regarding infections.
Leflunomide	Discontinue study treatment
Administration of any live or live-attenuated vaccine (including for measles) is prohibited while patients are exposed to study drug (long-lasting effects of the study drugs should be taken into consideration)	They may be administered when patients are no longer exposed to study drug. Consider risk/benefit and follow local labels

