5.6.6 Role of Key site personnel

Key site personnel include (but are not limited to) the following individuals:

Investigator

The Investigator will be responsible for:

- Overall conduct of the study at the study site including assigning per protocol required study staff
 - Management of the routine clinical care of the study patients
 - Administration and supervision of initial sc injections and training/supervision of ability to self/home-administer. The Investigator may delegate this responsibility to the Study Nurse/Study Coordinator as appropriate and permissible by local regulation
 - Confirmation of patient's eligibility for randomization
- 

- Administration of T25FW, 9HPT and SDMT (may be delegated to the Independent EDSS rater, a back-up physician, a Study Nurse/Study Coordinator or other accordingly experienced medical professionals)
- Referral of patients with neurological symptoms consistent with MS relapse to the Independent EDSS Rater
- Management of adverse events and MS relapses
- Review of patient diaries
- Ensuring that all site personnel are informed of concomitant medications excluded per protocol (e.g. the use of systemic steroids other than for the treatment of MS relapses or as pre-medication before injection)

It is strongly recommended that the Investigator remain unchanged throughout the entire course of the study. Occasionally, the Investigator may designate other medical personnel/health care professionals (other than the Independent EDSS Rater, e.g., a back-up physician or Study Nurse/Study Coordinator) at the study site to perform some of the tests and evaluations listed above. The Investigator is also responsible for ensuring access to appropriate expertise for consultation (e.g. infectious disease, ECG interpretation, mental health care) during the study as needed.

Independent EDSS Rater

The Independent EDSS Rater will be responsible for:

- Obtaining an EDSS score based on detailed neurological examination of patients with neurological symptoms consistent with MS relapse as referred by the Investigator at scheduled or unscheduled visits
- Obtaining an EDSS score based on detailed neurological examination at scheduled visits
- Administration of T25FW, 9HPT and SDMT if delegated by the Investigator and if experienced with the administration of these assessments

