For the first 3 injections, additional summaries will be provided by category of injection related premedication. Specifically, 9 categories are defined as 1) no injection related premedication, 2) type 1, 3) type 2, 4) type 3, 5) type 1+ type 2, 6) type 1+ type 3, 7) type 2+ type 3, 8) type 1+ type 2+ type 3, 9) Any injection related premedication. The types 1 to 3 refer to protocol specified three types of injection related premedication as stated in [Section 2.4.2.3](#).

A separate listing for injection site reaction AEs and injection systemic reaction AEs will be provided where all reported injection related reactions (IRR) (regardless of timing) will be listed along with the corresponding injection sequence number and time to onset from the most recent injection as well as from Day 1. The listing will be sorted by injection of first occurrence of symptoms. Specifically, under the first injection, patients whose first IRR was associated with the first injection will be listed; within a patient all IRRs to all injections will be listed chronologically. Under the second injection, patients whose first IRR was associated with the second injection will be listed; similarly, within a patient all IRRs to all injections will be listed chronologically. The listing will continue with subsequent injections until all patients with IRRs are included in the listing.

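### PPS rule COMD03 and protocol Table 5-1 omit the injection-premedication exemption in protocol 5.6.6, so the literal rule can remove patients who received the recommended first-injection steroid

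*SAP*

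**What the plan says.** Four places deal with systemic steroids during treatment.

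- **SAP 5.6, Table 5-7, COMD03** excludes from the PPS patients given "systemic corticosteroids (except when given for MS Relapse treatment) while taking double-blind treatment". The same section rests membership of the analysis sets wholly on the listed deviation and non-deviation criteria.
- **Protocol 5.5.8, Table 5-1** lists as prohibited: "Systemic corticosteroids (except for when given for MS relapse treatment as defined in Section 5.5.6". The general rule there is: "Use of excluded medications is not allowed after randomization while the patient is on study medication".
- **Protocol 5.5.7** states: "For the first injection only, the addition of premedication with steroids (methylprednisolone 100 mg iv or equivalent) is recommended". On timing it adds: "Premedication should be administered 30 to 60 minutes prior to study drug injection".
- **Protocol 5.6.6**, on the investigator's duty to brief site staff, gives as an example of excluded medication "the use of systemic steroids other than for the treatment of MS relapses or as pre-medication before injection". Premedication is therefore a second exemption there, and it is not limited to the first injection.

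The SAP holds premedication as its own subcategory of the concomitant medication data, with steroids as type 1 (2.4.2.3). It tabulates premedication by injection up to injection 10, and in 2.8.1.1.1 adds: "For the first 3 injections, additional summaries will be provided by category of injection related premedication".

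**The concern.** The PPS is meant to leave out patients whose major deviations could confound the full-analysis-set (FAS) results. A steroid that the protocol itself recommends with the first injection is not such a deviation, yet the wording of COMD03 catches it. Applied as written, the rule would select patients partly on whether their investigator declined a protocol recommendation, and it would shrink the PPS by an amount nobody has planned for.

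The PPS feeds the per-protocol repeat of the ARR model (SAP 2.5.5) and the per-protocol analyses of 3mCDW and 6mCDW on the two studies combined (SAP 2.6.2.1 and 2.6.3.1). The same omission in Table 5-1 also sets the protocol's list of prohibited medication against two of its other sections.

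**Working it through.** **1. The passages side by side.**

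| Place | Relapse treatment exempt | Injection premedication exempt |
|---|---|---|
| SAP Table 5-7, COMD03 | yes | no |
| Protocol Table 5-1 | yes | no |
| Protocol 5.6.6 | yes | yes, any injection |
| Protocol 5.5.7 | not addressed | steroid recommended, first injection only |

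**2. Does the SAP close the gap elsewhere?** The premedication subcategory is defined in 2.4.2.3, but Section 5.6 does not refer to it. SAP 2.4.2.1 leaves premedication out of the concomitant medication summary; it says nothing about deviation checks.

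**3. Does timing close it?** For the first injection, the steroid is due 30 to 60 minutes beforehand, so by the clock it precedes that injection. By date it does not: the SAP counts the on-treatment period in days from the first injection or first dose date (2.1.1), classifies medications by start and end dates (2.4.2.1), and matches premedication to the first injection by calendar day (2.4.2.3). The order of the first capsule and the premedication is not stated. No section says whether COMD03 is assigned by date or by clock time. For later injections the patient is already on double-blind treatment, so timing gives no protection.

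**4. Size.** The plan states no PPS size, exclusion rate or steroid uptake, so there is no figure to reproduce for the exclusion itself. On the literal date-based reading,

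excluded = assumed uptake × 900 (planned patients per study, SAP Section 3).

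25%: 0.25 × 900 = 225. 50%: 450. 75%: 675. For the combined disability analyses (2 × 900 = 1800 patients) the counts double to 450, 900 and 1350.

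**5. What that would do to the per-protocol ARR analysis.** Inputs from protocol 9.8.1: rates 0.168 and 0.28, T = 1.5 years, κ = 0.82, one-sided 0.025.

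V = 1/(0.168 × 1.5) + 1/(0.28 × 1.5) + 2 × 0.82 = 3.968 + 2.381 + 1.640 = 7.989.

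Check against the plan: n per arm = (1.960 + 1.282)² × V / (ln 0.6)² = 321.7, which rounds up to the stated 322; 644/0.8 = 805, also as stated.

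Power = Φ(|ln 0.6| / √(V/n) − 1.960), with n the number left per arm:

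| Assumed uptake | Left of 900 | Power, no dropout | Power, 20% dropout |
|---|---|---|---|
| 0% | 900 | 97% | 93% |
| 25% | 675 | 91% | 84% |
| 50% | 450 | 77% | 68% |
| 75% | 225 | 48% | 40% |

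This is an illustration: it borrows the planning assumptions for the FAS and ignores every other reason for leaving the PPS.

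**The case against.** The best defence is that the literal reading was never intended. Table 5-7 lists protocol deviations, and following a recommendation is not naturally one. Protocol 5.6.6 names premedication as an exception. Read literally, Table 5-1 would call for treatment interruption, and 5.6.2 lists use of a Table 5-1 treatment under permanent discontinuation, for a steroid recommended with the first injection; that looks like a missing cross-reference rather than a working rule. First-injection premedication is given blind in both arms before any injection reaction, so differential loss by arm is not expected from it. Deviations are fixed before unblinding and PPS exclusions are listed with reasons, so a mass exclusion would be seen.

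Much of this stands. It makes a literal application less likely and easier to detect. It does not change the wording on which SAP 5.6 makes classification depend, and it leaves to presumed intent a choice that should be written down. The point about balance between arms covers the first injection only. A steroid at a later injection can follow an earlier reaction, although the SAP's by-injection tables do not show that such use occurs or how often.

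A reader might infer that COMD03 would remove most patients. The documents do not support that. It needs uptake above 50%, and no uptake is given. The protocol says of acetaminophen and antihistamines that their use "is recommended and may be administered at the discretion of the Investigator"; the added steroid is likewise recommended, not required. Day 1 exclusion also depends on a date-based reading that the SAP's day-level definitions make plausible but do not establish for COMD03. Nor do the documents show that the remaining patients would be unrepresentative.

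**Conclusion.** The inconsistency is real. COMD03 and Table 5-1 lack an exemption that protocol 5.6.6 states and that the recommendation in 5.5.7 presupposes. Two consequences follow from the wording of COMD03:

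- if it is applied by date, every patient given the recommended first-injection steroid leaves the PPS;
- whether it is applied by date or by clock, every patient given steroid premedication at a later injection leaves the PPS.

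How many patients that means is unknown; the counts and power figures above rest entirely on assumed uptake. The reach is limited to supportive analyses: per-protocol ARR, 3mCDW and 6mCDW. No per-protocol analysis is specified for 6mCDI, so it would be too broad to say that all disability endpoints are affected. The primary ARR analysis and the confirmatory disability analyses use the FAS and are untouched. The point should be corrected because the correction is cheap and the rule conflicts with the protocol; it does not threaten the trial's main conclusions.

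**What to change.** In COMD03, extend the bracketed exemption with *or as injection-related premedication*, and identify those records by the existing *Injection related premedication* subcategory in the concomitant medication data. The cost is one phrase in the SAP; no new data are needed.

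The SAP's revision history already includes an addendum made after database lock, so classification may be complete. In that case the sponsor should document how COMD03 was applied, in particular whether any patient left the PPS for premedication alone and whether assignment was by date or by clock time.

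Separately, the wording of protocol Table 5-1, with the action it attaches to systemic corticosteroids and the related entry in 5.6.2, must be reconciled with 5.5.7 and 5.6.6. So must the difference between a recommendation limited to the first injection and an exemption without that limit. Which clinical rule is right is for the sponsor to settle. The cost is an alignment of protocol wording.

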5.7 Statistical method details for TEAEs

5.7.1 Odds ratios and 95% confidence interval

For an investigational drug group with n_1 patients at risk, independent from the control group with n_0 patients at risk, of whom x_1 and x_0 experience a certain event with probability π_1 and π_0 respectively, the odds ratio (OR) is estimated as

$$\frac{p_1 / (1 - p_1)}{p_0 / (1 - p_0)} \quad \text{with } p_1 = x_1/n_1 \text{ and } p_0 = x_0/n_0, \text{ simplifying to } \frac{x_1 \times (n_0 - x_0)}{x_0 \times (n_1 - x_1)}.$$

The OR and a conditional exact 95% confidence interval will be obtained by using the SAS procedure PROC FREQ with statement EXACT OR. The data set will include a patient level response variable indicating whether a patient has at least one AE of a specific type (1=yes, 0=no).

By default SAS sets the OR to missing if the odds for one of the treatments cannot be calculated (no infinity in SAS). This is problematic as infrequent but very serious adverse events that happen exclusively on active treatment can easily be missed if the OR for such highly imbalanced events is set to missing and sorted last. To ensure that potentially important imbalances appear at the top of a table if it is sorted by OR, the following additional rules are applied (considering the numerator and the denominator of the OR that would lead to divisions by zero):

- NO CASE CLAUSE [0/0]: If ($x_1=0$ and $x_0=0$) or ($x_1=n_1$ and $x_0=n_0$), i.e. there are either no events in both treatment groups, or all patients in both treatment groups had the event, then the OR cannot be estimated. The OR can be left missing for the sorting, but should be displayed on the output as “N.E.” indicating not estimable (if it has to be shown on the table, in this case it needs to be explained in the footnote).
- SAFETY CLAUSE[~/0]: If ($x_0=0$ and $x_1 \neq 0$) or ($x_0 \neq n_0$ and $x_1=n_1$), i.e. there are no events on control, but some on investigational drug, or everyone on investigational drug experienced the event, but not everyone on control, then OR will be imputed as 100000 for the sorting (so that it comes up top if sorted by the OR). On the output present the OR as “>100”.
- EFFICACY CLAUSE[0/~]: If ($x_1=0$ and $x_0 \neq 0$) or ($x_1 \neq n_1$ and $x_0=n_0$), i.e. there are no events on investigational drug, but some on control, or everyone on control experienced the event, but not everyone on investigational drug, then OR will be imputed as

1/100000 for the sorting (so that it comes prior to the missing ones). On the output present the OR as “<1/100”.

5.7.2 Exposure adjusted incidence rate and 95% confidence interval

It will be assumed that for each of n patients in a clinical trial the time t_j ($j=1, \dots, n$) to the first incidence of a certain event is observed, or if the event was not experienced, the time is censored at the end of the observation period. The sequence of first occurrences of an event will be modeled to follow approximately a Poisson process θ with constant intensity λ . The rate parameter λ will be estimated by $\hat{\lambda} = \frac{D}{T}$, where $T = \sum_{j=1}^n t_j$ and D is the number of patients with at least one event. Conditionally on T, an exact 95% confidence interval for a Poisson variable with parameter θT and observed value D can be obtained based on ([Garwood, 1936](#)), from which an exact 95% confidence interval for $\hat{\lambda} = \frac{D}{T}$ will be derived as follows ([Sahai, 1993](#); [Ulm, 1990](#)):

Lower confidence limit $L = \frac{0.5c_{\alpha/2, 2D}}{T}$ for $D > 0$, 0 otherwise,

Upper confidence limit $U = \frac{0.5c_{1-\alpha/2, 2D+2}}{T}$

where $c_{\alpha, k}$ is the α^{th} quantile of the Chi-square distribution with k degrees of freedom.

The SAS procedure GENMOD will be used to fit a Poisson regression model with only treatment as factor, the log-link and natural logarithm of time as the offset variable. The incidence rate (and 95% confidence intervals) are obtained as the exponentiated estimates by treatment (e.g. obtained by statement LSMEANS with option EXP). The data set will include a patient level response variable indicating whether the patient experienced at least one event of a specific type (1=yes, 0=no) and a patient level time variable which is derived as follows:

- For patients who had at least one event of that type: time is calculated as (start day of the first event - date of first administration of study drug+1).
- For patients who did not have an event of that type: time at risk as defined in [Section 2.4.1](#) will be used.

The time will be divided by 365.25 before taking the logarithm transformation as offset variable so that the estimated incidence rate corresponds to an annualized rate.

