take into account the time-at-risk as defined in [Section 2.4.1](#) for each patient. The incidence rate ratios (investigational drug vs. control) and corresponding 95% confidence intervals will be presented along with this summary. Details in calculations of incidence rates and their 95% confidence intervals as well as incidence rate ratios and their 95% confidence intervals are provided in [Section 5.7.2](#). The exposure adjusted incidence rates provide appropriate inferences for events that are likely to occur at any time during the observation period with constant risk over time (e.g., infection or cancer).

If a patient reported more than one adverse event within the same primary system organ class, the patient will be counted only once with the maximum CTCAE grade at the system organ class level, where applicable.

All AEs will be presented in listings.

For the subgroup of patients who accidentally received both investigational drug and active comparator during the study, a listing of adverse events along with drug administration information will be provided.

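### SAP 5.7.2 prescribes two incompatible 95% intervals for the same exposure-adjusted adverse event rate; the model-based one, and the rate-ratio interval that depends on it, cannot be used when an arm has no event

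*SAP*

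**What the plan says.** SAP 5.7.2 defines the rate as D/T, where "D is the number of patients with at least one event" and T is the summed time at risk. It then describes an interval in two ways.

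- **Exact.** "Conditionally on T, an exact 95% confidence interval for a Poisson variable" is inverted to give limits for the rate, using chi-square quantiles with 2D and 2D+2 degrees of freedom. The lower limit has its own zero-event rule: "for $D > 0$, 0 otherwise".
- **Model-based.** "The SAS procedure GENMOD will be used to fit a Poisson regression model with only treatment as factor", with a log link and log time as offset. The text continues: "The incidence rate (and 95% confidence intervals) are obtained as the exponentiated estimates by treatment", naming LSMEANS with the EXP option as an example.

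The section does not say which interval goes into the tables.

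On the comparison between arms, SAP 2.8.1 says: "The incidence rate ratios (investigational drug vs. control) and corresponding 95% confidence intervals will be presented along with this summary". It refers the reader to 5.7.2 for the calculation, but 5.7.2 gives no ratio formula. SAP 2.8.1 and 2.8.1.1 apply these rates to all TEAEs, serious TEAEs and events of special interest, down to preferred term.

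For odds ratios, SAP 5.7.1 addresses zero cells directly: "This is problematic as infrequent but very serious adverse events that happen exclusively on active treatment can easily be missed". It gives display and sorting rules for them.

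**The concern.** The second description reads like the software implementation of the first, but it computes something else. A programmer cannot follow both, and two competent programmers could produce different safety tables from the same text. The difference is largest where counts are small, which is where a rare harm would first appear. When one arm has no event, the model has no finite estimate on the log scale, so the model interval for that arm and the interval for the ratio both fail.

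SAP 2.8.1 makes this more than a formality. It names exposure-adjusted rates as the suitable measure for events with constant risk over time, giving infection and cancer as examples. Specific malignancies and serious infections, tabulated by preferred term, are plausible candidates for zero or very small counts in one arm.

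**Working it through.** The plan gives no numerical result here, so there is no figure to reproduce. The check is to write out both methods and compare them.

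**Inputs.** D, T, the chi-square limits and the GENMOD specification come from SAP 5.7.2. For illustration, person-time per arm is 450 patients (SAP section 3) × 1.5 years (SAP 3.1.1.1) = 675 patient-years. Adding the full 100-day safety window of SAP 2.4.1 gives 450 × (1.5 + 100/365.25) = 798 patient-years. Both values are assumptions; actual follow-up varies.

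**Formulae for one arm.**

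- Exact: lower 0.5 × χ²(0.025; 2D)/T, or 0 if D = 0; upper 0.5 × χ²(0.975; 2D+2)/T.
- Model: with treatment as the only factor, the estimated log rate is log(D/T) with standard error 1/√D. The limits are therefore (D/T) × exp(±1.96/√D), undefined at D = 0.

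**Results in units of events/T.**

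| D | Exact | Wald |
|---|---|---|
| 0 | 0 to 3.69 | none |
| 1 | 0.03 to 5.57 | 0.14 to 7.10 |
| 3 | 0.62 to 8.77 | 0.97 to 9.30 |

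**Results per 100 patient-years, T = 675.**

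| D | Exact | Wald |
|---|---|---|
| 0 | 0 to 0.547 | none |
| 1 | 0.004 to 0.825 | 0.021 to 1.052 |
| 5 | 0.241 to 1.729 | 0.308 to 1.780 |
| 100 | 12.05 to 18.02 | 12.18 to 18.02 |

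Both Wald limits lie above the exact ones at small D, and the gap is negligible for common events. At 798 patient-years the exact upper limit for D = 0 is 0.462.

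**Model fit with an empty arm.** A patient-level Poisson regression was run (450 per arm, 1.5 years each, in statsmodels rather than SAS).

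- 5 events versus 0: the empty arm's log rate stopped at −26.3 with a standard error of about 11,949. Its rate is effectively 0, with an interval from 0 to effectively infinity. The ratio came out at 1.9 × 10⁹, also with an interval from 0 to effectively infinity. The arm with five events was unaffected: 0.741 per 100 patient-years, 0.308 to 1.780.
- 0 versus 0: the fit failed.

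SAS may print different digits or a warning, but the cause is the same: the maximum likelihood estimate lies at minus infinity.

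**What an exact ratio interval would give.** Conditional on D1 + D0, D1 is binomial with odds equal to the rate ratio × T1/T0. Take Clopper-Pearson limits p for this binomial probability and convert each to p/(1−p) × T0/T1. With equal person-time:

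- 5 versus 3: 0.32 to 10.73. The model gives 1.667 × exp(±1.96 × √(1/5 + 1/3)) = 0.40 to 6.97.
- 5 versus 0: lower p = 0.025^(1/5) = 0.478, so 0.478/0.522 = 0.92; the interval is 0.92 to infinity.
- 6 versus 0: lower p = 0.025^(1/6) = 0.541, so 0.541/0.459 = 1.18; the interval is 1.18 to infinity.

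**How often an arm is empty.** If an arm expects 1, 2 or 3 events, the chance of none is exp(−1) = 37%, exp(−2) = 14% or exp(−3) = 5%. These expected counts are illustrative; the documents do not predict counts by preferred term.

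**The case against.** The strongest reply is that a reader could infer more from this conflict than the documents support. Four such readings fail.

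- *The plan has no rule for zero events.* It has one for the single-arm rate: D/T is 0, the exact lower limit is set to 0, and the upper limit is finite. Only the ratio lacks a rule.
- *No result is usable when an arm is empty.* The empty arm's rate is 0 by definition and would print as about 0 from the model. The other arm keeps its rate and interval.
- *The printed intervals will be wrong.* That assumes the GENMOD limits are the ones tabulated. The same section says that the exact limits will be derived, so the defect is an unresolved choice.
- *Events seen only on ofatumumab would go unnoticed.* SAP 2.8.1 and 2.8.1.1 also plan crude incidence with odds ratios for all, serious and special-interest TEAEs. SAP 5.7.1 gives these conditional exact intervals and zero-cell rules that display such events as above 100 and place them first when sorted by odds ratio. All adverse events are listed as well.

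It can also be said that an exact ratio interval adds little in the sparsest rows. With equal person-time and five or fewer events in total it cannot exclude 1 (5 versus 0 gives a lower limit of 0.92, 0 versus 5 an upper limit of 1.09), and with no control event the point estimate is infinite under any method.

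All of this stands and limits the point. It does not remove the contradiction between the two intervals or supply the missing ratio method.

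**Conclusion.** The point holds as an internal contradiction and a gap. SAP 5.7.2 prescribes exact and Wald limits for the same rate without choosing between them. It also leaves the rate-ratio interval promised in SAP 2.8.1 to a model fit that breaks down when either arm is empty.

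The effect is confined to sparse rows of descriptive safety tables. It is visible at one to five events, negligible by about 100, and total only for the empty arm's model interval and the ratio interval. No primary or key secondary test, type I error or sample size is touched.

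The odds-ratio tables are a real safeguard but not a full substitute, because SAP 2.8.1 itself prefers exposure-adjusted rates for constant-risk events such as infection or cancer. The rate-per-patient-year figures rest on the assumed 675 to 798 patient-years per arm; the comparison in events/T does not. The ratio examples assume equal person-time. That sparse rows will occur is a reasonable expectation, not a documented count.

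**What to change.** 1. In SAP 5.7.2, state that the exact chi-square limits already given there are the reported intervals for each arm's rate, and remove the GENMOD least-squares-means intervals.
2. Add a method for the rate ratio: exact conditional (binomial) limits given D1 + D0 and the two person-times.
3. Extend the zero-event display and sorting rules of SAP 5.7.1 to the ratio. When control has no event and ofatumumab has some, print the lower limit and infinity and sort the row to the top. When neither arm has an event, show the ratio as not estimable.

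The cost is programming only; no new data are needed. The downside is that exact limits are conservative. With equal person-time, six events against none are needed before the ratio interval excludes 1, and the table footnote should say that an interval including 1 in such rows is not evidence of no difference.
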